### 3.7 Sample size estimation

The sample size in this study is estimated by using the formula for hypothesis tests for two population proportions (two-sided test)

$$n = \frac{\left\{ Z_{1-\alpha/2} \sqrt{2\bar{P}(1-\bar{P})} + Z_{1-\beta} \sqrt{P_1(1-P_1) + P_2(1-P_2)} \right\}^2}{(P_1 - P_2)^2}$$

details:

$\alpha$  : 5

$1-\beta$  : 90

$P_1$  : 0.15

$P_2$  : 0.05

$n$  : 376

From the equation above, it is estimated for the sample size of the study to be 376 samples, with estimated drop out proportion of 10%, it is deduced the sample size of 414 samples.

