### Introduction

#### 1.1 Background

Nowadays, a high volume of cardiac surgery has been performed at National Cardiovascular Centre Harapan Kita, Jakarta, Indonesia. In 2017 there were 1721 cardiac surgery conducted in the adult cardiac surgery division. Of those, 801 were coronary artery bypass graft surgeries, 598 were heart valve repair and replacement surgeries, 93 were vascular surgeries, 116 were congenital cardiac surgeries, 8 surgeries in intracardiac tumour, and 105 other cardiac surgeries.

In cardiac surgeries, the current approach established is through median sternotomy. The sternum consists of a low vascularized tissue and it may be damaged especially when internal thoracic arteries are used for coronary artery bypass grafting. Thus, the postoperative complication related to sternal healing are common. The sternotomy wound may be complicated with partial or complete sternal dehiscence and sternal wound infection, osteomyelitis or even mediastinitis. Surgical site infection (SSI) involving the sternum is a distressing complication in cardiac surgery. The incidence of postoperative superficial and deep SSI in cardiac surgery varies from 1.3 to 12.8%.

Subsequent to median sternotomy, bone wax has been applied for decades as a mechanical barrier to maintain the haemostasis on the surface edges of the sternum. Bone wax is a nonabsorbable substance and it is believed that bone wax may cause inflammation as it is produced foreign body reaction and mechanically inhibit osteoblastic activity, which may eventually lead to increased risk of postoperative sternal dehiscence. Apparently, the use of bone wax has no clear recommendation in any guidelines and there are still controversies regarding the efficacy and safety of the application of bone wax.

To overcome the problem that may be related to the use of bone wax. Different innovative approaches are evaluated, including, a non-woven material to protect the sternum during operation. Sternum Guard™ is a single use, sterile surgical drape, for sternal protection,

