## **1.4 Hypothesis**

We hypothesize that Sternum Guard™ is more effective than Bone Wax in reducing surgical site infection and sternal dehiscence for post cardiac surgery patients.

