**Specific Objectives:**

1. To compare the surgical site infection and sternal dehiscence rates at the end of hospital stay, day 14 post operation, and day 30 post operation in post cardiac surgery patient with the application of Sternum Guard™ as opposed to bone wax intraoperatively.
2. To compare the haemostasis effect of Sternum Guard™ as opposed to bone wax intraoperatively in cardiac surgery.
3. To compare the satisfaction rate (includes global satisfaction rate, haemostasis and dryness of surgical site, and mechanical protection) of the surgeons who are using the Sternum Guard™ as opposed to bone wax intraoperatively in cardiac surgery.

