### **2.3 Complications following median sternotomy**

Sternal wound complications following median sternotomy remain a challenge in cardiac surgery with a severe burden for the patient and high costs for health care providers. According to previous studies, superficial problems occurred in 1.1–6.7% whereas the incidence of deep sternal wound complications ranged from 0.1 to 3.7%.

A change in the spectrum of cardiac surgery has been observed in recent years. Patients are older, suffer more frequently from diabetes mellitus and have a higher average body mass index (BMI). There is a decreasing number of surgical bypass grafts accompanied by a trend towards more valve operations and complex procedures. In addition, the frequency of emergency procedures is rising.

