### **2.4 Surgical site infection**

Over 234 million surgeries are performed around the world every year, yet despite the remarkable advances in surgical technologies and anaesthetic techniques, surgical site infections (SSIs) remain a major cause of patient morbidity and mortality. SSIs are potential complications associated with any surgical procedure; however, they are the most preventable hospital acquired infection (HAI). It is estimated that SSI will occur in up to 9.5% of inpatient surgical procedures. SSI is defined as any infection occurring within 30 days after surgery or within 12 months of surgical implantation of a prosthesis or foreign body.

Millions of surgical procedures are conducted around the world each year. Most procedures result in surgical wounds that heal by primary intention, where wound edges are re-approximated using sutures, staples, clips or glue. Some surgical wounds are left open to heal (where closure is not appropriate because of infection, physical impossibility of approximating wound edges or because of the need to allow drainage) and some wounds break down following closure; these open wounds heal from the 'bottom-up' (known as 'healing by secondary intention').

Surgical wounds are at risk from microbial contamination and thus possible infection. Contamination may originate from the patient, for example when microbes on the skin enter a wound, or from the surrounding environment, for example from operating staff, the theatre, or wider hospital and home environments. SSI was identified as the leading cause of hospital-acquired infection in a systematic review of studies in low-and middle-income countries.

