## **2.6 Deep sternal wound infection**

[figure not shown]
Deep sternal wound infection (DSWI) is a serious postoperative complication of cardiac surgery. According to the literature, the incidence of DSWI after cardiac surgery has been variously reported as between 0.8 and 5.0%. This postoperative complication is a serious one, being responsible for a mortality rate varies between 19% and 29% in different series of adult cardiac surgical patients. Based on JACVSD registered data from 2004 to 2009, the overall incidence of DSWI after cardiac surgery was 1.8%, as for each operative procedure, the incidence of postoperative DSWI was 1.8% in isolated CABG group, 1.3% in valve group, 2.8% in valve with CABG group, 1.9% in thoracic aorta group and 3.4% in thoracic aorta with CABG group. When operative procedure concomitant with CABG was done, the incidence of postoperative DSWI showed 1.5% of elevation compared with isolated original valve and thoracic aortic procedure. Internal thoracic artery use, prolonged operative time and longer cardiopulmonary bypass time are possible mechanisms to explain these increased rates of DSWI.

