## **2.7 Sternal dehiscence**

[figure not shown]
Sternal Dehiscence is a serious complication of cardiac surgery which is often a predecessor to mediastinitis, in fact it is often accompanied with mediastinitis. The incidence of sternal dehiscence after median sternotomy is varied between 0.5% to 8.4%. Sternal dehiscence is defined as the separation of the edges of the sternum from one to another and can occur in the absence of soft tissue dehiscence. This condition can be caused by wire fracture, loosening, or “puling through” the sternal edges.

Patients may complain of a painful chest motion and “clicking”. The diagnosis is made upon physical examination by placing each hand on either side of the sternum and having the patient cough, which will cause a click or “rocking” of the sternum^64. Sternal dehiscence is a surgical emergency as the complication may include an increased risk of ventricular rupture due to sharp wires or bone fragments rubbing against the heart. When sternal dehiscence occurs in the early postoperative period, the patient is taken to the operating room for exploration.

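### Section 3.7 claims 90% power for 15% versus 5% without naming the endpoint or a source; at the plan's highest cited rates, power is about 84–95% for SSI and 66% for sternal dehiscence

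*Combined protocol and SAP*

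**What the plan says.** Section 3.7 (Sample size estimation) uses the two-sided formula for two proportions with alpha 5%, power 90%, P1 = 0.15 and P2 = 0.05. It states that "it is estimated for the sample size of the study to be 376 samples, with estimated drop out proportion of 10"%, and arrives at 414. It names no outcome for P1 and P2 and cites no source.

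The hypothesis (section 1.4) is that Sternum Guard is "more effective than Bone Wax in reducing surgical site infection and sternal dehiscence for post cardiac surgery patients". The first specific objective (section 1.5) compares both outcomes "at the end of hospital stay, day 14 post operation, and day 30 post operation". Table 1 codes SSI and dehiscence as separate variables. Table 3 lists SSI, dehiscence, haemostasis and satisfaction under one primary-outcomes label.

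The incidences that the plan cites are:

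- Section 1.1: "The incidence of postoperative superficial and deep SSI in cardiac surgery varies from 1.3 to 12.8"%.
- Section 2.4: "It is estimated that SSI will occur in up to 9.5% of inpatient surgical procedures".
- Section 2.7: "The incidence of sternal dehiscence after median sternotomy is varied between 0.5% to 8.4"%.
- Section 2.6: "the incidence of DSWI after cardiac surgery has been variously reported as between 0.8 and 5.0"%.
- Section 2.3: "the incidence of deep sternal wound complications ranged from 0.1 to 3.7"%. The same sentence gives 1.1–6.7% for superficial wound problems, which it does not label as SSI.

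**The concern.** The 90% power belongs to a pair of rates, and the plan does not attach that pair to an outcome. None of the cited SSI or dehiscence incidences reaches 15%. (The 19–29% in section 2.6 is mortality.) If the true event rate is lower and the relative benefit is as planned, there are fewer events and less power than stated.

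This matters most for dehiscence, which the hypothesis puts on an equal footing with SSI. Section 3.9 plans tests at p < 0.05 and mentions no confidence intervals. A non-significant dehiscence result could then be read as showing no difference in a trial described as having 90% power.

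**Working it through.** **Inputs.** Two-sided alpha 5%, power 90%, P1 = 0.15 and P2 = 0.05 come from section 3.7. The top SSI rate of 12.8% is from section 1.1 and the top dehiscence rate of 8.4% from section 2.7. The allocation ratio is not stated. I take 1:1, because Table 6 budgets 207 devices, half of 414.

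**The plan's own figure.** With the printed formula and mean proportion (0.15 + 0.05)/2 = 0.10:

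- 1.960 × √(2 × 0.10 × 0.90) = 0.8315
- 1.282 × √(0.15 × 0.85 + 0.05 × 0.95) = 0.5361
- n = (0.8315 + 0.5361)² / 0.10² = 187.05, so 188 per arm and 376 in total.

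The figure reproduces, with 376 as the two-arm total.

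**Power at other rates.** Solving the same formula for power at 188 per arm:

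z = [(P1 − P2)√188 − 1.960√(2P̄(1 − P̄))] / √(P1(1 − P1) + P2(1 − P2)), and power = Φ(z).

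The planned effect can be carried over as a two-thirds relative reduction (P2 = P1/3) or as a 10-point drop (P2 = P1 − 0.10).

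| Outcome and effect | P1 vs P2 | z | Power |
|---|---|---|---|
| As planned | 15% vs 5% | (1.3711 − 0.8315)/0.4183 = 1.290 | 90.1% |
| SSI, two-thirds reduction | 12.8% vs 4.27% | (1.1700 − 0.7744)/0.3905 = 1.013 | 84.5% |
| SSI, 10-point drop | 12.8% vs 2.8% | (1.3711 − 0.7433)/0.3726 = 1.685 | 95.4% |
| SSI, P2 left at 5% | 12.8% vs 5% | (1.0695 − 0.7893)/0.3989 = 0.703 | 75.9% |
| Dehiscence, two-thirds reduction | 8.4% vs 2.8% | (0.7678 − 0.6373)/0.3227 = 0.404 | 65.7% |
| Dehiscence, 10-point drop | 8.4% vs below zero | – | not possible |

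Both rates are the tops of their ranges, so under a fixed relative reduction every lower cited rate gives less power. The 9.5% inpatient SSI rate gives 71%. The bottoms of the ranges give 15% (SSI at 1.3%) and 8% (dehiscence at 0.5%).

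**Sensitivity to the test and to N.** For 8.4% vs 2.8%, exact power at 188 per arm is 67% with the uncorrected chi-square and 59% with Fisher's test. For 12.8% vs 4.27% it is 86% and 82%. If all 207 per arm were analysed, the formula gives 69.9% for dehiscence and 87.7% (two-thirds reduction) or 96.9% (10-point drop) for SSI.

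**Precision.** The approximate 95% CI half-width for the risk difference is 1.96√[(P1(1 − P1) + P2(1 − P2))/188]. It is 5.6 points for 12.8% vs 4.27% and 4.6 points for 8.4% vs 2.8%.

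**Drop-out.** 376 × 1.10 = 413.6, hence 414. Losing 10% of 414 leaves 372.6, about 372 or 186 per arm, with 89.8% power at 15% vs 5%. To keep 376 evaluable, 376/0.90 = 417.8, so 418.

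**The case against.** The strongest reply is that 15% may be a reasonable rate for this trial. The cited ranges cover cardiac or inpatient surgery in general, not an arm in which every patient receives bone wax, and the plan's premise (sections 1.1 and 2.5) is that bone wax may raise risk. The gap to 12.8% is only 2.2 points. Section 3.10 also places dehiscence inside the item headed surgical site infection, so a combined endpoint may be intended, and 15% would be more plausible for that. This stands as far as it goes: the documents do not show that 15% is wrong. But they give no basis for it and define no combined endpoint.

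The arm and the horizon can also be inferred. The hypothesis implies that 15% is bone wax and 5% Sternum Guard. The 30-day SSI definitions (section 2.4) and the day-30 loss-to-follow-up rule (section 3.4) point to day 30. That reply succeeds. What remains missing is the endpoint and the source.

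A reader might infer that a composite settles the matter by adding the two top rates, 12.8 + 8.4 = 21.2%. The documents do not support this. They cite no such rate, and they describe overlap: section 2.7 says dehiscence often comes with mediastinitis, and section 2.4 lists spontaneous opening of a deep incision among the deep SSI criteria.

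Finally, a null result is better judged by its confidence interval than by planned power. That is true, but section 3.9 plans no interval.

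**Conclusion.** The point holds in a limited form. The sample size arithmetic is correct, but the 90% is not attached to a named endpoint, and its 15% lies above every SSI or dehiscence incidence cited. At 188 evaluable per arm, power for SSI at 12.8% is about 84% or 95%, depending on whether the relative or the absolute effect is kept (76% if P2 stays at 5%). For dehiscence at 8.4% it is about 66% under the two-thirds reduction. So 90% is not reached for dehiscence at any cited rate under the planned relative effect, and for SSI it is reached only under some assumptions.

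These figures assume 1:1 allocation, the printed normal approximation, and an effect carried over from 15% vs 5%. Three stronger readings should be avoided:

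- The trial is not shown to be underpowered for SSI, since one natural reading gives 95%.
- The 66% is not a floor, because it belongs to the top cited dehiscence rate.
- Section 1.2 does not bear on local event rates. The gap it describes is in evidence on the device's efficacy.

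The drop-out slip is minor, at 89.8% against a 90% target.

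**What to change.** In section 3.7:

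- Tie the 90% to one named endpoint at day 30, and give the source or local data behind 15% and 5%.
- State that 376 is the two-arm total.
- Restate power at 188 evaluable per arm: for any SSI at 12.8%, 84% with a two-thirds reduction and 95% with a 10-point drop; for dehiscence at 8.4%, 66% with a two-thirds reduction.
- Say that dehiscence alone is not powered at 90% at the cited rates under the planned relative effect.
- If SSI-or-dehiscence is the intended endpoint, define it and justify its rate, allowing for overlap. Do not use the 21.2% sum.
- State that 414 leaves about 372 evaluable (89.8% power at 15% vs 5%), or use 418.

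In section 3.9, report the risk difference with its 95% CI for SSI and for dehiscence alongside each p-value.

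The cost is a few sentences and two intervals, with no added patients if 414 is kept, or 4 more for 418. The downside is that the stated power becomes less favourable. Holding 90% for SSI at 12.8% with a two-thirds reduction would instead need 224 per arm, so 448 evaluable, or 448/0.90 = 498 randomised.

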#### **3.3 Sample and population**

The participant in this study will be recruited from the adult cardiac surgery division at the National Cardiovascular Centre Harapan Kita, Jakarta, Indonesia. All participants will be selected randomly and are eligible for cardiac surgery. Participants then will undergo an eligibility assessment based on the inclusion and exclusion criteria. Afterwards, the participants that are qualified for this study will be divided into two groups (control vs treatment group) randomly.

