#### **3.4 Inclusion and exclusion criteria**

Inclusion Criteria:

1. Patients ages > 18 years old
2. Patients who are scheduled electively for cardiac surgery
3. Cardiac surgery with the usage of cardiopulmonary bypass machine
4. Patients who are agreed to participate in this study

Exclusion Criteria:

1. Patients who are scheduled for surgery in emergency or urgent manner
2. Patients with the history of uncontrolled hypertension and uncontrolled diabetes mellitus.
3. Patients with the history of past cardiac surgery

Drop – out Criteria:

1. Patients who are pronounced death on operation table
2. Patients who are pronounced death within hospitalization
3. Patients who are lost to follow up (Day 30 post-operative)
4. Patients who are not committed for the whole stage of the research

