### **3.9 Data analysis**

All collected data will be verified and will be statistically analyzed using SPSS and the result from the data analysis was considered statistically significant with a p-value of  $< 0.05$ . For descriptive analysis, we will perform the analysis independently for numerical and categorical data. All numerical data will be analyzed using Coefficient of Variance and confirmed by Kolmogorov-Smirnov normality test. Normally distributed data will be analyzed using mean and standard deviation, meanwhile the abnormally distributed data will be analyzed using median, minimum value and maximum value. Categorical data analysis will be presented by percentage and frequencies table.

For inferential data analysis, we will perform the comparison tests and mean comparison test. The proportion comparison tests are applied for comparing categorical independence variable between Sternum Guard™ and bone wax group, such as Chi-square test and Fisher's Exact test as an alternative for chi-squared test. Mean comparison tests are utilized for comparing numerical independence variable between Sternum Guard™ and bone wax group, such as Independent T-Test and Mann-Whitney test for the non-parametric test.

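### The 10% drop-out allowance is applied as 376 × 1.10 = 414; keeping 376 evaluable patients at 10% loss needs 376 / 0.90 = 418

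*Combined protocol and SAP*

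**What the plan says.** Section 3.7 of the combined protocol and SAP uses the "formula for hypothesis tests for two population proportions (two-sided test"), with alpha 5%, power 90%, and event proportions of 0.15 and 0.05. From this, "it is estimated for the sample size of the study to be 376 samples". The drop-out allowance follows in the same sentence: "with estimated drop out proportion of 10%, it is deduced the sample size of 414 samples". No inflation formula is written out, and the section does not say whether 376 is per arm or in total.

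Three other places bear on the point:

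- Section 3.3 says that qualifying participants "will be divided into two groups (control vs treatment group) randomly".
- Section 3.4 lists the drop-out criteria: death on the operating table, death in hospital, loss to follow-up by Day 30, and lack of commitment to the full study.
- Table 6 in the Appendix budgets for 207 Sternum Guard devices, which is half of 414.

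**The concern.** A drop-out proportion normally means the share of enrolled patients who are lost. To end with a required number after losing a share d of those enrolled, the required number is divided by (1 − d). Multiplying by (1 + d) takes the share of the smaller, evaluable number and gives too few patients. The figure of 414 looks like the second calculation.

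This inflation is the plan's only stated provision for attrition, and 414 is the working recruitment target that the device count follows. If the step is wrong, the plan states a tolerance for loss that its own sample size does not provide.

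**Working it through.** **Inputs**

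- Two-sided alpha 0.05: section 3.7 gives a two-sided test at 5, read as 5%. Section 3.9 agrees, since results are "considered statistically significant with a p-value of" less than 0.05.
- Power 0.90, P1 = 0.15, P2 = 0.05, and so P̄ = 0.10: section 3.7.
- Drop-out proportion 0.10: section 3.7.
- Equal allocation: inferred from the two randomised groups and the 207 devices (414 / 2). No ratio is stated.

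**Step 1. Reproduce 376.** The plan's formula is

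n = {Z(1−α/2) √[2P̄(1−P̄)] + Z(1−β) √[P1(1−P1) + P2(1−P2)]}² / (P1 − P2)²

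- First term: 1.960 × √(2 × 0.10 × 0.90) = 1.960 × √0.18 = 0.8315
- Second term: 1.2816 × √(0.1275 + 0.0475) = 1.2816 × √0.175 = 0.5361
- n = (0.8315 + 0.5361)² / 0.01 = 187.05, rounded up to 188 per arm
- Total: 2 × 188 = 376

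This matches the plan, so 376 is the total for both arms.

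**Step 2. Reproduce 414.** 376 × 1.10 = 413.6, rounded up to 414. This also matches.

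**Step 3. Apply the stated loss to 414.** 414 × 0.90 = 372.6, or about 186 per arm. That is 376 − 372.6 = 3.4 patients short.

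**Step 4. The size that preserves 376.** 376 / 0.90 = 417.8, rounded up to 418, or 209 per arm. Check: 418 × 0.90 = 376.2.

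**Step 5. The loss that 414 does allow.** 1 − 376 / 414 = 9.2%.

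**Step 6. Effect on power.** Solving the plan's formula for power gives Φ{[0.10 √n − 0.8315] / √0.175}:

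| Evaluable per arm | Power |
|---|---|
| 186 | 89.8% |
| 186.3 (= 372.6 / 2) | 89.9% |
| 187 | 90.0% (0.8999) |
| 188 | 90.1% |

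**Step 7. Could 414 come from another route?** Adding a continuity correction to the formula gives 207 per arm, which is 414 in total. But the printed formula has no such correction, its result is 376, and the text attributes the rise to drop-out. On that route there would be no drop-out allowance at all, so the coincidence does not explain the figure.

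**The case against.** The strongest reply concerns size. The 376 is already rounded up in each arm. The unrounded requirement is 2 × 187.05 = 374.1, and against that the 372.6 remaining is short by only 1.5 patients. Power at 372.6 is 89.9%, about 0.1 point under the target, and 414 tolerates 1 − 374.1 / 414 = 9.6% loss before power falls below 90%. The gap is also smaller than the uncertainty in the allowance. If each of 414 patients independently has a 10% chance of dropping out, the number lost has a standard deviation of √(414 × 0.10 × 0.90) = 6.1, and the 10% is itself a round figure with no source given. All of this stands. It keeps the point minor and rules out any claim that the trial is underpowered. It does not make the sentence correct, because even the unrounded requirement needs 374.1 / 0.90 = 415.7, so 416 patients.

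A second reply is that no inflation formula is written, so the 10% could be an addition to the required number, which makes 414 exact. That reading fits poorly with the term drop-out proportion, and with section 3.4, where every listed drop-out is a loss of someone already a participant, for example "Patients who are lost to follow up (Day 30 post-operative").

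It is also fair to say that 188 per arm is not printed in the plan. It is a deduction, supported by the exact reproduction of 376 and by the device count.

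**Conclusion.** The concern holds. As written, 414 does not keep 376 evaluable patients at 10% loss; it leaves about 372. The size is small: a difference of 4 in the enrolment figure (418 against 414), and about 0.3 point of power (89.8% at 186 per arm against 90.1% at 188). No test, endpoint or analysis population depends on it.

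The conclusion rests on equal allocation, on 376 being the total, and on the 10% being a share of enrolled patients. The documents support all three, though none is stated outright. It takes the 15% and 5% event proportions as given.

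**What to change.** Correct the one line in section 3.7 in one of these ways:

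- Keep 414 and state that it preserves 376 evaluable patients for losses of up to 9.2%.
- Keep 414 and state that a 10% loss would leave about 372 evaluable patients, with about 89.8% power.
- Write 376 / 0.90 = 418, or 209 per arm.

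Either of the first two is enough. They need no extra patients or devices, and their only cost is a slightly less favourable stated tolerance. The third adds 4 patients and raises the device count in Table 6 from 207 to 209.

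Whichever is chosen, write out the inflation formula and say that the two-proportion formula gives 188 per arm and 376 in total, so that a reader can trace the figure.
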